4.5.2 Medical History and Demographic Data

Medical history includes clinically significant diseases, procedures, use of alcohol and drugs of abuse within the past year, and medication allergies. In particular, sites should record whether the patient has any history of FVIII inhibitor, anaphylaxis or known thrombophilia. It should also include all medication taken in the 4 weeks prior to screening (including prescription, over-the-counter, and herbal/homeopathic remedies and therapies) or in the 24 weeks prior to screening for medications intended to treat osteopenia or osteoporosis. If imaging tests of bone health (e.g., densitometry, dual energy X-ray absorptiometry [DEXA]) were performed in the year prior to screening, the results should be recorded. Finally, number of bleeds during the 24 weeks prior to study enrollment should be documented, as well as the number of school/work days missed and number of days hospitalized during the 24 weeks prior to study entry.

Demographic data will include age, sex, and self-reported race and ethnicity.

4.5.3 Physical Examinations

A complete physical examination should include but not necessarily be limited to the evaluation of head, eye, ear, nose, and throat and include cardiovascular, dermatological, musculoskeletal (including HJHS; see [Appendix 8](#)), respiratory, gastrointestinal, and neurological systems, height, and weight. Any abnormality identified during screening should be recorded on the General Medical History and Baseline Conditions eCRF. Subsequently, a targeted (i.e., musculoskeletal,

dermatological) and/or symptom-driven examination should be conducted as noted in the schedule of assessments or as clinically indicated. New or worsened abnormalities from screening should be recorded as adverse events. A complete physical examination will be performed at screening and at least targeted physical examinations will be performed at subsequent visits.

4.5.4 Vital Signs

Vital signs will include measurement of heart and respiratory rate, temperature, systolic and diastolic blood pressure, and weight and should be recorded before study drug administration. Frequency of vital sign assessments should follow the schedule of assessments but may also be taken anytime as unscheduled assessments as judged by the investigator.

4.5.5 Laboratory, Biomarker, and Other Biological Samples

Local laboratory assessments will be performed as indicated on the schedule of assessments. When study drug administration is scheduled on days of clinic visit, laboratory samples should be drawn before the administration of study drug. Laboratory assessments will include the following:

- Hematology (hemoglobin, hematocrit, platelet count, RBC count, WBC count, absolute differential count [neutrophils, eosinophils, lymphocytes, monocytes, basophils, other cells], mean corpuscular volume, mean corpuscular hemoglobin, mean corpuscular hemoglobin concentration, and RBC distribution width)
- Serum chemistries, (sodium, potassium, chloride, glucose, blood urea nitrogen, creatinine, calcium, phosphorus, magnesium, total and direct bilirubin, total protein, albumin, alanine aminotransferase, aspartate aminotransferase, lactate dehydrogenase, alkaline phosphatase, creatine phosphokinase, and uric acid).
- Pregnancy test: All women of childbearing potential (including those who have had a tubal ligation) will have a serum pregnancy test at screening and within 7 days prior to initiation of study medication, if applicable.

Urine pregnancy tests will be performed at specified subsequent visits. If a urine pregnancy test result is positive, it must be confirmed by a serum pregnancy test.

The following samples will be sent to the Sponsor or a designee for centralized analysis:

- Plasma samples for PK analysis
- Plasma samples for immunogenicity assessment (ADA)
- Serum and plasma for PD and exploratory PD biomarker assessments (aPTT, PT, FVIII activity, and others as listed in [Appendix 2](#))
- Plasma samples for anti-FVIII antibody measurement (inhibitor titer) will be sent to the Sponsor throughout the study, with the exception of the test needed at screening for patients who do not have a documented negative inhibitor test (<0.6 BU) within 8 weeks prior to enrollment.

4.5.6 Electrocardiograms

ECG recordings will be obtained at study sites at specified timepoints, as outlined in the schedule of assessments (see [Appendix 1](#)).

All ECG recordings must be performed using a standard high-quality, high-fidelity digital electrocardiograph machine equipped with computer-based interval measurements. Lead placement should be as consistent as possible. The following parameters will be obtained: QT, RR, HR, QTcB, QTcF, PR and QRS and T- and U-wave morphology. ECG recordings must be performed after the patient has been resting in a supine position for at least 10 minutes.

All ECGs are to be obtained prior to other procedures scheduled at that same time (e.g., vital sign measurements, blood draws) and ideally should not be obtained within 3 hours after any meal. Circumstances that may induce changes in heart rate, including environmental distractions (e.g., television, radio, conversation) should be avoided during the pre-ECG resting period and during ECG recording.

Any ECG changes that are deemed clinically significant by the investigator (e.g., associated with symptoms or lead to a change in study treatment or concomitant treatment, or discontinuation from study treatment), must be reported as an adverse event on the adverse event eCRF. The investigator or designee must review, sign, and date all ECG tracings. The ECG may be repeated if investigator deems it appropriate. Paper copies will be kept as part of the patient's permanent study file at the site.

4.5.7 Electronic Patient-Reported Outcomes

Patient reported data will be collected electronically using two devices: a personal handheld mobile device for the Bleed/Medication Questionnaire and a tablet at study sites for HRQoL questionnaires. To capture bleed data, emicizumab use, and other hemophilia medication use during study treatment, patients will complete the Bleed/Medication Questionnaire on a handheld device that will be provided to them during the Week 1 visit at the study site. This device will remain with the patient for the duration of the study to enter bleed and medication data weekly at a minimum. Patients who withdraw from emicizumab treatment will continue to record bleeds and hemophilia medication administration until they complete the safety follow-up visit. In addition, at specified visits, patients will complete HRQoL, health status, and satisfaction/preference questionnaires on a tablet device that will remain at study sites. The instructions for completing the patient-reported outcome (PRO) questionnaires electronically will be provided by the investigator staff during the Week 1 visit at the site. The data will be transmitted automatically after entry to a centralized secure database at the vendor. Of note, if the electronic data collection system becomes unavailable, the Sponsor may instruct sites to collect PRO data (bleed data, emicizumab use, hemophilia medication use, and HRQoL) on paper.

HRQoL:

The Haem-A-QoL and the Haemo-QoL-SF will be used to measure HRQoL in adults and adolescents, respectively (see [Appendix 3](#) and [Appendix 4](#)). The Haem-A-QoL was designed for adult patients with hemophilia. It consists of 46 items comprising 10 dimensions (physical health, feelings, view, sport and leisure time, work and school, dealing, treatment, future, family planning, and relationships/partners) and a scale representing total score. Items are rated along 5 response options, although for some items there is also a 'not applicable' option (von Mackensen and Gringeri 2005; 2010).

The Haemo-QoL has been developed in a series of age-related questionnaires to measure HRQoL in children and adolescents with hemophilia (Bullinger et al. 2002; von Mackensen and Bullinger 2004; Pollak et al. 2006). These versions include a 77-item long form, a 35-item as well as a 16-item short form, and an 8-item index form. The short version for older children containing 35 items was selected for this study. This version covers nine dimensions considered relevant for the children's HRQoL (physical health, feelings, view of yourself, family, friends, other people, sports and school, dealing with hemophilia and treatment). Items are rated with five respective response options: never, seldom, sometimes, often, and always. Higher scores for both HRQoL measures are indicative of poorer HRQoL.

Health Status:

The EQ-5D-5L (see [Appendix 5](#)) is a generic, preference-based health utility measure that assesses health status and is used to inform pharmacoeconomic evaluations. The EQ-5D-5L consists of two parts. The first part, health state classification, contains five dimensions of health: mobility, self-care, usual activities, pain/discomfort, and anxiety/depression (Herdman et al. 2011; Janssen et al. 2013). Published weights are available that allow for the creation of a single summary score. Overall scores typically range from 0 to 1, although a score below 0 is theoretically possible representing a state worse than death, with low scores representing a higher level of dysfunction. The second part is a 0 to 100-point visual analog scale (VAS) that assesses current health status; higher scores are reflective of better health.

Patient Preference and Satisfaction:

Patient preference and satisfaction will be assessed through two measures. Preference for emicizumab treatment will be assessed through the Preference Survey, which asks patients to report which treatment they would prefer to continue to receive after having been treated with IV FVIII (episodic or prophylaxis) and SC emicizumab. Patients who express a preference are then asked to identify which reasons may have influenced their decision and indicate the top three reasons for their choice. Patients in Arms A, B, or D will complete the Patient Preference Survey at Week 17 on emicizumab. In addition, understanding the preference and satisfaction of patients who were previously on FVIII prophylaxis is of particular interest. Patients in Arm D will complete the Patient Satisfaction questionnaire, SQ-ISHI, at baseline and at the Week 21 or 25 visit. This 13-item measure was designed to assess satisfaction with SC emicizumab or with IV

FVIII prophylaxis by probing the general concepts of discomfort, worry, and difficulty with injections; confidence with treatment; duration, and frequency of treatment; ease of treatment; impact on daily activities; adherence; and overall satisfaction.

Missed Days of School or Work

Patients will also be asked to document the number of days of school or work missed in the previous 4 weeks at the timepoints outlined in the schedule of assessments (see [Appendix 1](#)).

4.5.8 Definitions

DEFINITION OF A BLEED

For the purposes of the efficacy analyses, a standardized definition of bleed, adapted from criteria defined by the Subcommittee on Standards and Criteria, FVIII/FIX subcommittee of the International Society of Thrombosis and Hemostasis, and similar to that used in a recent clinical study, will also be utilized in this study (Blanchette et al. 2014; Mahlangu et al. 2014).

An event is considered a treated bleed if coagulation factors are administered to treat signs or symptoms of bleeding (e.g., pain, swelling, etc.).

- Bleeds starting from the first sign of bleed and ending 72 hours after the last treatment for the bleed, within which any symptoms of bleeding at the same location or injections are ≤ 72 hours apart, are considered the same bleed.
- Any injection to treat the bleed, taken > 72 hours after the preceding injection, is considered the first injection to treat a new bleed at the same location.
- Any bleed at a different location is considered a separate bleed regardless of time from last injection.

An additional definition of all bleeds (i.e., both treated and not treated with coagulation factors) will be applied for certain secondary efficacy analyses.

DEFINITIONS OF BLEED SITES

- Target joints: defined as a major joint (e.g., hip, elbow, wrist, shoulder, knee, and ankle) into which repeated bleeds occur (frequency of ≥ 3 bleeds into the same joint over the last 24 weeks prior to study entry)
- Joint bleeds (sites per the Bleed/Medication Questionnaire)
- Muscle bleeds (sites as per the Bleed/Medication Questionnaire)
- Other bleeds (sites as per the Bleed/Medication Questionnaire)

DEFINITIONS OF BLEED TYPES

In addition, the assessment of a bleed will be separated into spontaneous bleeds, traumatic bleeds, and bleeds related to procedure/surgery. Both spontaneous bleeds (i.e., the occurrence of hemorrhage where neither the patient nor a caregiver can identify a reason) and traumatic bleeds (i.e., hemorrhage occurring secondary to an event such as trauma, “strenuous” activity, or “overuse”) will be collected.

- Spontaneous bleeds: Bleeds should be classified as spontaneous if a patient records a bleed when there is no known contributing factor such as definite trauma, antecedent “strenuous” activity or “overuse” or “procedure/surgery.” The determination of what constitutes “strenuous” or “overuse” will be at the discretion of the patient. For example, light jogging may be considered “non-strenuous” while sprinting may be considered “strenuous,” lifting of weights for a short period of time may be considered “moderate use” while repetitive weightlifting may be considered “overuse.”
- Traumatic bleeds: Bleeds should be classified as traumatic if a patient records a bleed when there is a known or believed reason for the bleed. For example, if a patient were to exercise “strenuously” and then have a bleed in the absence of any obvious injury, the bleed would be recorded as a traumatic bleed because, although no injury occurred, there was antecedent “strenuous” activity. Bleeds subsequent to injuries would certainly be classified as traumatic.
- Bleeds related to procedure/surgery: such as hematomas resulting from any surgeries or invasive procedures (e.g., tooth extractions, venipuncture, or SC drug administrations) or invasive diagnostic procedures (e.g., lumbar puncture, arterial blood gas determination, or any endoscopy with biopsy, etc.) would not be counted as bleeds but will be collected on the Bleed/Medication Questionnaire. Bleeds related to procedure/surgery are not associated with any trauma except procedure/surgery-induced trauma.

Patients (or patient’s legally authorized representative) will complete an electronic Bleed/Medication Questionnaire whenever a bleed occurs, or at least weekly to confirm all bleeds have been recorded. For each bleeding episode, they will provide information on the above topics as well as on the medication used to treat the bleed. Hemophilia medications that were taken will also be collected through the Bleed/Medication Questionnaire.

4.5.9 Activity Assessments

Patients who chose to participate in this part of the study should wear the study device while awake every day during three 2-week periods in the study: Weeks 1–2, Weeks 23–24, and Weeks 47–48. Patients will be instructed to wear the accelerometer on an elastic belt (supplied with the device) at the natural waistline on the right hip in line with the right axilla upon arising in the morning and continuously until retiring at night for 14 consecutive days. Patients will be instructed to charge the device weekly. A valid day of monitoring is defined as 10 or more wear hours per day. Wear time will be determined by subtracting non-wear time from 24 hours. Non-wear is defined by an

interval of at least 60 consecutive minutes of zero activity intensity counts, with allowance for 1–2 minutes of counts between 0 and 100. To provide reliable estimates, analyses will be restricted to participants with at least 8 valid days of accelerometer monitoring during each observation period (Troiano et al. 2008; Ahn et al. 2015).

The data will be collected using the study device to provide daily measures of DSC: DSC, mean activity (counts [cts]/min), peak activity (the largest activity value [cts/min]), and total activity counts (total cts/min over a 24-hour period) recorded each day. Mean daily activity is the average of the activity counts among all epochs (e.g., 1-minute period) that falls within the active periods during a 24-hour period.

An activity count is a measure of the acceleration that is measured by the device. The device measures acceleration as the sum of the maximum acceleration values each second during the epoch (acceleration is sampled 30 times/second). While DSC will be referenced as the primary physical activity measurement, it should be noted that activity counts (total, mean, and peak) do provide a secondary alternative for measuring physical activity relevant to the magnitude of energy expended by the subject. While DSC might provide more reliable correlation data, activity counts can help identify the possibility of increased activity intensity in the event that DSC remains relatively unchanged over time.

The number of hours the device was worn each day will also be derived from the activity counts data.

Patients will return their devices to the respective site at Weeks 3, 25, and 49 in order for the site to transfer the data from the device to the database.

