Participants will be instructed to wear the device for 2 weeks at the beginning of the study and for 2 weeks approximately every 6 months subsequently. Intermittent sampling of approximately a week was commonly employed in similar studies that assessed physical activity in patients with chronic diseases (Lavie et al. 1992; Watz et al. 2014; Ahn et al. 2015; Chu et al 2015; Yu et al. 2015). The incremental added value of additional days of data collection (Briscoe et al. 2014) is likely offset by diminishing compliance with a longer observation period. Due to logistical considerations, baseline activity will be captured during the first 2 weeks after enrollment rather than prior to starting treatment. Although patients will have started emicizumab, its level will be below steady state, and the relatively short duration on emicizumab at this time is unlikely to inspire a change in activity habits. Therefore, activity during Weeks 1 and 2 is expected to be similar to pre-study activity, and a change, if any, from pre-enrollment will likely only underestimate the effect of emicizumab rather than overestimate it. The alternative approach of delaying initiation of therapy to allow measurement of baseline DSC may be unacceptable to many patients and investigators.

The purpose of this activity assessment in this study is to evaluate the effects of emicizumab treatment on patients' DSC as measured by a waist-worn ActiGraph (a medical device used to continuously monitor and measure activity through a triaxial accelerometer) in patients with hemophilia A. The data collected by the study device will be scored to identify active and rest periods for each patient within each 24-hour period. This device continuously captures frequency, duration, and intensity of acceleration and through a proprietary algorithm converts the pattern of motion into step counts and activity counts (a value used to quantify both intensity and duration of physical activity). Although steps are not counted directly, the number of steps for each individual can be reliably derived from data obtained by a waist-worn device (Gironda et al. 2007; Garriguet et al. 2015). In general, the available technology is well suited to accurately capture DSC (Case et al. 2015), supporting its use in this study.

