6.8 EXPLORATORY ANALYSES

Summary statistics of the number of work/school days missed and days hospitalized will be presented by treatment arm. Summary statistics will also be presented for the SQ-ISHI and emicizumab Preference Survey. PD parameters (e.g., aPTT, parameters derived from thrombin generation, FVIII activity) and markers related to bone and joint health will be presented using summary statistics, including arithmetic and geometric means, median, range, standard deviations, and coefficients of variation.

For the activity assessment all enrolled subjects that contribute reliable activity data (i.e., at least 8 valid days) will be analyzed. There will be no imputation of missing data. Subjects will be grouped according to the treatment regimen to which they are assigned in the main study. Because of the exploratory nature of the study, there will be no type-1 error control for multiplicity. Enrollment, discontinuations, protocol violations/deviations, and duration of activity monitoring follow-up will be summarized. Demographic and baseline characteristics, such as age, sex, race/ethnicity, and weight will be summarized using descriptive statistics. Relative change is defined as

$$100 \times (DSC_{\text{Week } n} - DSC_{\text{baseline}}) / DSC_{\text{baseline}}$$

Relative change from baseline at Week 25 or 49 in mean DSC and activity counts (total, mean, and peak) will be calculated within each treatment group provided the patient has reported data on at least 8 days within the 14 day observation period. Subject-level averages at each timepoint will be presented via dot-plots and descriptive statistics by treatment group.

The main comparisons will be within-patient changes, calculated within each treatment group. Within the control arm, where patients are expected to switch to emicizumab prophylaxis treatment at 24 weeks, an additional comparison of the relative change from Week 25 to Week 49 will be performed.

Formal statistical modeling may be performed as appropriate. Such analysis will be based on between-treatment comparisons of the change in activity from baseline to Week 25 between patients receiving emicizumab prophylaxis (Arms A or B) versus no prophylaxis (Arm C).

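### Protocol 6.8 compares daily step count between periods without saying how wear hours are used, so a change in hours worn can read as a change in activity (minor, exploratory)

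*Protocol*

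**What the plan says.** Protocol 4.5.9 (Activity Assessments) asks participants to wear the device "upon arising in the morning and continuously until retiring at night for 14 consecutive days", in each of three windows: Weeks 1–2, 23–24 and 47–48. The rule for a usable day is "A valid day of monitoring is defined as 10 or more wear hours per day". For a usable window, "analyses will be restricted to participants with at least 8 valid days of accelerometer monitoring during each observation period". Non-wear is inferred from at least 60 consecutive minutes of zero counts, with a small allowance. The section also states: "The number of hours the device was worn each day will also be derived from the activity counts data".

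On the measures, 4.5.9 says "While DSC will be referenced as the primary physical activity measurement", with total, mean and peak activity counts as secondary alternatives. One of these is not a daily total: "Mean daily activity is the average of the activity counts among all epochs (e.g., 1-minute period) that falls within the active periods".

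Protocol 6.8 (Exploratory Analyses) states "Relative change from baseline at Week 25 or 49 in mean DSC and activity counts (total, mean, and peak) will be calculated". Its formula is 100 × (DSC at Week n − DSC at baseline) / DSC at baseline. The main comparisons are within-patient changes inside each treatment group, with an extra Week 25 to Week 49 comparison in Arm C. Modelling of Arms A or B against Arm C is optional, and its covariates are not named. Section 6.8 lists several items to be summarised for the activity part; wear hours are not among them.

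**The concern.** The 10-hour rule is a floor, not a standardisation. A 10-hour day and a 14-hour day both count in full, yet a daily total rises and falls with the hours in which steps can be recorded. The formula in 6.8 therefore combines two things: how active the patient was, and for how long the device was there to record it.

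The layout of the comparisons gives limited protection. A shift in wear time shared by all arms does not cancel in a within-arm change. Arm D has no concurrent control, and the extra Arm C comparison is also within arm. Only the optional comparison of Arms A or B with Arm C would remove most of a shared shift.

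What is at stake is how the lead activity result is read. Protocol 1.3 hypothesises that activity will increase, and 3.3.7 prefers the device partly because questionnaires miss modest changes in daily activity. Without wear hours beside the step counts, a reader cannot tell a modest change in activity from a modest change in wear.

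**Working it through.** The documents give no DSC mean, SD, effect size or wear hours, and Protocol 6.1 says that no data exist for a sample-size calculation. There is therefore no planned figure to reproduce. The check applies the formula in Protocol 6.8 to assumed wear times.

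**Inputs**
- From 4.5.9: any day of 10 or more wear hours is valid.
- From 6.8: the relative-change formula, with no wear-time term.
- Assumed: H0 = mean daily wear at baseline, H1 = mean daily wear at follow-up, and f = step rate in the lost hours divided by the day's average step rate. Step rates do not truly change.

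**1. Apparent change in DSC with no change in activity.** Relative change = −100 × f × (H0 − H1) / H0.
- 14 to 13 h, f = 1: −100 × 1/14 = −7.1%.
- 14 to 12 h, f = 1: −100 × 2/14 = −14.3%. With f = 0.5 it is −7.1%, and with f = 0.25 it is −3.6%.
- 14 to 10 h, the floor on average: −28.6% (f = 1), −14.3% (f = 0.5), −7.1% (f = 0.25).
- The reverse also holds. From 12 to 14 h with an even step rate, DSC rises by 100 × 2/12 = 16.7%.

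**2. A true increase of 10% in step rate (f = 1).** Observed change = 100 × (1.1 × H1/H0 − 1).
- 14 to 13 h: +2.1%.
- 14 to 12 h: −5.7%, so the sign reverses.

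**3. Optional comparison with Arm C.** Suppose the true change is +10% in Arm A or B and 0% in Arm C, and wear falls by the same ratio w = H1/H0 in both. Observed difference = 100 × (1.1w − w) = 10w points.
- 14 to 13 h: 9.3 points.
- 14 to 12 h: 8.6 points.

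A shared fall shrinks the difference but does not reverse it.

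**4. Steps per wear hour under the same assumptions.** Change = 100 × [(1 − f(H0 − H1)/H0) × H0/H1 − 1].
- f = 1: 0% in every case, so the correction is exact.
- 14 to 10 h, f = 0.5: 0.857 × 1.4 − 1 = +20%, against −14.3% for DSC.
- 14 to 10 h, f = 0.25: 0.929 × 1.4 − 1 = +30%, against −7.1% for DSC.
- For 14 to 10 h the two errors are equal in size when 4f/14 = 0.4 − 0.4f, that is at f ≈ 0.58. Below that value the adjusted measure is further from the truth than DSC, and in the opposite direction.

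**The case against.** The strongest reply is that the omission is not proven for the plan as a whole. SAP 2.2.3 and 4.2.8 are blacked out, as are parts of 2.3.3 and 4.5.3. In the SAP synopsis a redaction covers the place where the protocol's matching sentence refers to activity level. A reader might infer that the plan never adjusts for wear. The documents do not support this, because the gap is visible only in Protocol 6.8. This part of the reply stands.

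A reader might also infer that wear will fall over time, so that every arm is biased downward, and might cite 3.3.7 in support. The remark there, that the value of extra days "is likely offset by diminishing compliance with a longer observation period", concerns adding days to a single window. All three windows last two weeks, and nothing in the documents predicts fewer hours per day in the later ones. The direction is unknown. Likewise, the study is open label and the device optional, so wear could differ by arm, but no passage shows that it will.

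Third, mean counts per minute is already planned and does not scale with hours worn. That stands and helps the reader, but it does not correct DSC or total counts.

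Fourth, adjustment has its own faults. Step 4 of the working shows over-correction when the lost hours are quiet. Non-wear is itself inferred from inactivity, and a longer active day gives more wear hours, so adjusting can remove real change. This also stands. A reader might conclude that steps per wear hour should replace DSC; these points argue against it.

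Finally, single-day contrasts such as 16 h against 10 h (−37.5%) overstate the matter, since the analysis averages at least 8 valid days per window.

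**Conclusion.** The concern holds for Protocol 6.8. The comparison of mean DSC and total counts across the three windows carries no wear-time term, although wear hours are derived daily and the valid-day rule sets only a minimum. Because the main comparisons are within arm, a change in wear in either direction reads as a change in activity.

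The size is conditional. With an unchanged step rate, a shift in mean wear of 1 to 2 hours from 14 h moves DSC by 7.1% to 14.3% if the lost hours are of average activity, and by less if they are quieter. These wear hours are assumptions, and the actual shift could be nil.

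This is a minor point. Participation is optional, the objective is exploratory with no type I error control, and no primary, secondary or safety conclusion depends on it.

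**What to change.** Unless the redacted SAP text already does so, add the following to Protocol 6.8 or the matching SAP section:

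- Keep DSC as the lead activity measure, analysed as now described.
- Tabulate mean daily wear hours on valid days, by arm and by window.
- Pre-specify a supporting analysis of DSC and total counts that accounts for wear time: steps (or counts) per wear hour for the within-patient changes, and wear hours as a covariate in a sensitivity version of any model of Arm A or B against Arm C.
- State that these results are read alongside mean counts per minute. If wear hours are stable across windows, the unadjusted DSC can be taken at face value in this respect. If they are not, the unadjusted and adjusted results are reported together.

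The cost is one table and a small amount of extra analysis; no new data are collected. The drawback is that the adjusted result can err the other way when the lost hours are quiet or when inactivity is scored as non-wear, which is why it should remain supporting.
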